**Study Address:**

**University of Texas MD Anderson Cancer Center [name]**

**AIM:** To evaluate the 25-gauge needle for usability, sample adequacy and diagnostic yield and compare it to the currently used 22-gauge needle.

## **1. Background**

EBUS-TBNA is a minimally invasive technique that has become standard of care for mediastinal staging of patients with Non Small Cell Lung Cancer. It has been traditionally performed with 22-gauge needles with an excellent diagnostic accuracy and safety profile. Although many have postulated that larger needle channels would increase diagnostic yield, the use of a 21 gauge needle has been shown to reduce sample quality due to excessive blood within the aspirate without effecting diagnostic yield. In fact, a meta-analysis of Endoscopic Ultrasound guided biopsy in solid pancreatic lesions suggested that a smaller 25-gauge needle improves sensitivity for malignancy in comparison to a standard 22-gauge needle. This phenomenon of improving sample adequacy with smaller needle biopsies has also been seen in ultrasonography-guided fine-needle biopsy of the thyroid. Recently, a new 25-gauge EBUS needle (Boston Scientific, Natick, MA, USA) has become available, but no studies so far have compared the utility of this needle with the standard 22-gauge needle for EBUS-TBNA.

**2. Objectives:** To evaluate the utility of the 25-gauge needle relative to the traditionally used 22-gauge needle for sample adequacy and diagnostic yield during EBUS bronchoscopy.

**2.1.** Primary outcome: To determine the degree of concordance in determining sample adequacy and diagnostic yield between the 25-gauge and 22-gauge needle after using 2 passes with each needle size.

**2.2.** Secondary outcomes

- To assess the diagnostic yield obtained with each needle size
- To assess the concordance between each needle size based on diagnostic yield
- To evaluate EBUS-TBNA related complications with each needle size
- To evaluate differences in usability of the different needle sizes, and identify specific lymph node stations that might be more challenging as identified by Likert scale recorded by physicians.

**3. Study Population:** An estimated 120 patients with suspicion of either benign or malignant disease in mediastinal or hilar lymph nodes undergoing EBUS-TBNA for diagnostic purposes or mediastinal staging.

**3.1. Inclusion criteria:**

- 1) Age 18 years or older
- 2) Indication for EBUS-guided needle biopsy based on suspicion of either benign or malignant disease in mediastinal or hilar lymph nodes.

**3.2. Exclusion Criteria:**

- 1) Patients who are pregnant or lactating
- 2) Inability to give informed consent
- 3) Patients in which only one lymph node station is expected to be sampled by the performing clinician.

**4. Research Plan and Methods:**

- 4.1. Study Design: This is a prospective cohort study.
- 4.2. Patients with suspected or confirmed early stage lung cancer who require EBUS-TBNA as part of their staging process and patients with mediastinal or hilar adenopathy undergoing diagnostic EBUS-TBNA are eligible to participate.
- 4.3. EBUS-TBNA will be performed at MD Anderson Cancer Center as per our standard clinical protocol as follows:
  - 4.3.1. Conventional flexible bronchoscopy will first be performed to examine the tracheobronchial tree, followed by examination of the intra-thoracic lymph nodes using a linear array ultrasound bronchoscope.
  - 4.3.2. For patients undergoing EBUS-TBNA for evaluation of targeted radiographically abnormal lymph nodes, directed ultrasonographic evaluation of suspicious lymph nodes will be performed prior to biopsy.
  - 4.3.3. In patients undergoing EBUS-TBNA for mediastinal staging of lung cancer a complete screening of mediastinal and hilar lymph nodes will be performed to identify those meeting criteria for sampling.
    - 4.3.3.1. Ultrasound criteria for sampling: size > 0.5 mm OR a combination of features that are associated with malignancy (sharp margins, heterogeneity, central necrosis sign and rounded shape).
  - 4.3.4. Nodal sampling will begin on the side opposite to the primary tumor to avoid the possibility of cross-contamination of specimens and resulting staging inaccuracies.
- 4.4. Once lymph nodes are identified which require sampling a minimum of five total passes will be performed with the following protocol: Note: concordance as described by the primary outcome will be assessed using needle passes 1, 2, 4 and 5, where the first needle size will correspond to passes 1 & 2 and the second needle size will correspond to passes 4 & 5. Because a total of 5 passes will be conducted:
  - 4.4.1. (Passes 1, 2, & 3): Three initial needle passes from a lymph node will be performed with either the 22-G or 25-G needle depending on the order of the needle size used first determined by randomization. However, only needle passes 1 & 2 will be used for analysis purposes.
  - 4.4.2. (Passes 4 & 5): Two final needle passes will be performed on the lymph node with the other needle, once all lymph node sampling with the first needle size is complete.
  - 4.4.3. The order in which the needles will be used will be determined by randomization. The randomization will be carried out on a per patient basis.
- 4.5. Randomization: We will use the CORe system for randomization of needle size (25-G vs 22-G) order on a per patient basis.
- 4.6. For each specimen collected, as per our standard practice the stylet will be replaced through the needle lumen to push the sample in a slide. The slide will be smeared with a second slide. One of the slides will be stained with Diff quick method and the other with PAP. The remaining tissue will be pushed with a syringe and collected in a liquid medium containing RPMI.
- 4.7. For each station and each needle, the performing physician will rate their subjective experience on a five point Likert scale to assess the following characteristics: 1) ease of needle insertion through the scope, 2) bronchoscopic visibility of needle sheath, 3) scope flexibility following needle insertion into working

channel, 4) ultrasound image quality following needle insertion into working channel, 5) ease of needle puncture, 6) visibility of needle during puncture, and 7) ease of needle removal from the scope.

**4.8.** As per our standard practice, each needle pass will be submitted to cytology to assess the adequacy of the sample and diagnostic interpretation.

**4.8.1.** Cytology results will be categorized into one of the following five groups: inadequate material (defined as having a predominance of blood or bronchial epithelial cells), normal lymphoid tissue, granulomatous inflammation, necrosis, and malignancy.

**4.8.2.** Samples will be ranked from worst to best as inadequate material, necrosis, normal lymphoid tissue, granulomatous inflammation and malignancy. For every lymph node, we will select the best sample for each sampling technique.

**4.8.3.** For the outcome of sample adequacy and for determining concordance between the two needle sizes, we will dichotomize results as either "inadequate" (inadequate material) or "adequate" (normal lymphoid tissue, granulomatous inflammation, necrosis, or malignancy).

**4.8.4.** To determine the concordance between the two needle sizes on diagnosis, we will dichotomize results as either "diagnostic" (granulomatous inflammation, normal lymphoid tissue, or malignancy) or "nondiagnostic" (inadequate material or necrosis).

**4.8.5.** Each needle sample will also be assessed by cytologist for quality using the Mair's scoring system with values range from 0 to 10 and are classified as follows: 0 to 2= poor; 3 to 6=good; and 7 to 10= superior.

**4.8.6.** For study purposes, we will be computing concordance using the aggregate sample adequacy from the 2 needle passes pertaining to each (the 22 and 25-gauge) needle size.

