**Fig 1: Bronchoscopists data collection sheet**

|   |  |   |   |   |   |   |
|---|--|---|---|---|---|---|
| LN station:   |  |   |   |   |   |   |
| Size on CT (mm)   |  |   |   |   |   |   |
| Size on EBUS (mm)   |  |   |   |   |   |   |
| Pass number:  |  | 1 | 2 | 3 | 4 | 5 |
| Needle size: (22/25)  |  |   |   |   |   |   |
| Suction: (y/n)  |  |   |   |   |   |   |
| Bronchoscopist assessment items are scored from 1-5 as follows:
1= very poor, 2= poor, 3= adequate 4= good 5= excellent          |  |   |   |   |   |   |
| Ease of needle insertion  |  |   |   |   |   |   |
| visibility of needle sheath   |  |   |   |   |   |   |
| scope flexibility following needle insertion  |  |   |   |   |   |   |
| ultrasound image quality following needle insertion   |  |   |   |   |   |   |
| ease of needle puncture   |  |   |   |   |   |   |
| visibility of needle during puncture  |  |   |   |   |   |   |
| ease of needle removal  |  |   |   |   |   |   |
| Cytological Assessment: 1= inadequate material 2= normal lymphoid tissue
3= granulomatous inflammation 4= necrosis 5= malignancy |  |   |   |   |   |   |
| Mair Score (See figure 2 below for reference)*  |  |   |   |   |   |   |

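### Nothing in the available text masks the cytologist to needle gauge or to a node's earlier reads, although the primary endpoint is agreement between those reads

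*Combined protocol and SAP*

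**What the plan says.** The primary outcome (section 2.1) is concordance between the two gauges on adequacy and diagnostic yield, two passes each. Section 4.4 takes passes 1 and 2 for the first needle and passes 4 and 5 for the second, from the same node. Passes 4 and 5 wait until sampling with the first needle is finished (4.4.2). On order, section 4.4.3 says: "The randomization will be carried out on a per patient basis".

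The data are cytology reads. Under 4.8, "each needle pass will be submitted to cytology to assess the adequacy of the sample and diagnostic interpretation". Section 4.8.1 has five categories, the lowest being "inadequate material (defined as having a predominance of blood or bronchial epithelial cells", with no numeric cut-off for predominance. Section 4.8.2 adds: "For every lymph node, we will select the best sample for each sampling technique". Section 4.8.6 confirms that "we will be computing concordance using the aggregate sample adequacy from the 2 needle passes" belonging to each gauge. On quality, 4.8.5 says: "Each needle sample will also be assessed by cytologist for quality using the Mair's scoring system". Section 5 lists a ROSE result for adequacy and for yield at every pass.

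No section says what the cytologist knows about gauge, pass order or the node's earlier results. The only mention of blinding is general REDCap text in 6.1 about data access between institutions. Section 8 plans a regression for sequence and period effects, and kappa and exact intervals for agreement.

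**The concern.** Success in this trial means high agreement, so the two reads of a node need to be independent of each other and of the gauge. Two kinds of knowledge threaten that.

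- **Gauge.** In the cells of Table 1, a stricter view of 25-G samples moves nodes from a to c and from b to d. A more lenient view moves them from c to a and from d to b. Concordance can fall or rise, and agreement on diagnosis and Mair category can be distorted in the same way.
- **The node's earlier result.** A reader who remembers it may repeat it. That raises concordance and favours rejecting H0.

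Randomising needle order balances which gauge comes first. Sequence and period terms estimate order effects. Neither removes dependence of the second read on the first.

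**Working it through.** **Inputs from the plan.** N = 200 nodes and H0: p ≤ 90% (section 7); alternative 96%, power 88%, final two-sided p-value 0.044 (Table 2).

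**Assumed inputs, in no document.** g is the share of concordant nodes turned discordant by knowledge of gauge. f is the share of discordant nodes pulled into agreement by knowledge of the earlier result.

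**Step 1: reproduce the plan.** z = (x/200 − 0.90)/√(0.90 × 0.10/200), with standard error 0.0212. For x = 188, z = 1.89 and two-sided p = 0.059. For x = 189, z = 2.12 and p = 0.034. The smallest successful count is therefore 189. With X ~ Bin(200, p), P(X ≥ 189) is 0.0168 at p = 0.90 and 0.8925 at p = 0.96. A simulation of all four looks, reading the Table 2 p-values as two-sided, gave power of 89.6% without futility stopping and 85.8% with it. The stated 88% lies between these and is not disputed. The corresponding rejection rates at p = 0.90 were 1.9% and 1.6%, close to the fixed-sample 1.7%.

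**Step 2: how few nodes separate the hypotheses.** Discordant nodes expected at 90%: 0.10 × 200 = 20. At 96%: 0.04 × 200 = 8. The gap is 12 nodes.

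**Step 3: gauge known.** Observed concordance = 0.96 × (1 − g).

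| g | Observed p | P(X ≥ 189) |
|---|---|---|
| 0 | 0.9600 | 89.3% |
| 1% | 0.9504 | 70.9% |
| 2% | 0.9408 | 47.7% |

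**Step 4: earlier result known.** Observed concordance = t + (1 − t) × f, where t is true concordance.

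| f | Observed p, t = 0.90 | P(X ≥ 189) | Observed p, t = 0.88 | P(X ≥ 189) |
|---|---|---|---|---|
| 0 | 0.900 | 1.7% | 0.880 | 0.15% |
| 10% | 0.910 | 4.7% | 0.892 | 0.7% |
| 20% | 0.920 | 11.7% | 0.904 | 2.6% |

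Steps 3 and 4 assume a fixed N of 200, no interim looks and independent nodes.

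**Step 5: which part each remedy reaches.** Hiding the gauge acts on g. It leaves f untouched at ROSE, because the reader there can still remember the node's earlier result. Only reads with pass, node and patient also hidden act on f.

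**The case against.** Several points on the other side are fair.

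- **Fig 1 does not show exposure.** It carries "Needle size: (22/25" above the row that begins "Cytological Assessment: 1= inadequate material 2= normal lymphoid tissue", so a reader might infer that the cytologist sees the gauge. Its title makes it the bronchoscopists' own sheet, where needle size is expected. It says nothing about what the cytologist sees, and the point does not rest on it.
- **Other nodes come between.** Under 4.4.2 the second needle waits for all first-needle sampling, and exclusion 3 removes patients expected to have only one station sampled. Other nodes' reads will therefore often fall between a node's two sets. That may weaken recall, but it is not masking.
- **Adequacy has a definition.** It does, and four of the five categories count as adequate (4.8.3). The definition still turns on a judgement of predominance.
- **Larger error rates can be produced.** Treating pulls on passes 4 and 5 as independent, with a 10% or 20% chance per read, gives false success of up to 7.2% or 21.8%. The documents do not support that independence: the same reader, node and earlier result would plausibly link the two pulls. If they are fully linked, the figures are the 4.7% and 11.7% above.
- **The cheap remedy misses recall at ROSE.** This stands, and it limits what the change can be said to achieve.

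**Conclusion.** The gap is real: the primary endpoint is same-node agreement between judgement-based reads, and no available text masks the reader to gauge or to earlier reads. Masking stated only in the front matter or the Figure 3 flow chart cannot be excluded.

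A reader might infer that reported concordance will be inflated, or that the type I error is wrong by a known amount. The documents support neither. They show no actual exposure, they give no value for g or f, and the two mechanisms can work in opposite directions. A reader might also infer a biased test of which needle scores higher on Mair, but section 8 plans only agreement measures for quality.

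The illustrations show sensitivity only: with 12 nodes separating the hypotheses, small shifts matter. The sample size and the stated power need no correction on this account. This is a cheap improvement to the design.

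**What to change.** In 4.8, require that slides from each pass reach the cytologist under a study code that hides needle gauge, at ROSE and at any later read. Record cytology category and Mair score on a cytology form with no needle-size field, linked to gauge only at analysis. Per-patient random order makes this workable: the reader may know that a pass belongs to the second needle without knowing its gauge.

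Where Mair or by-stain reads are made after the procedure anyway, also hide pass, node and patient, read the slides in mixed order, and report concordance from those reads as a sensitivity analysis. The documents do not say when these reads are made, and no new round of reads should be added for this purpose.

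State as a limitation that hiding the gauge at ROSE does not hide the node's earlier result. If masking is already practised, writing it into 4.8 is enough.

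Cost: code labels on up to 4 passes × 2 stains × 200 nodes = 1,600 analysed slides, and one extra form to handle. Pass 3 slides should not reveal the first needle's gauge either, which adds up to 1 × 2 × 200 = 400 labels. No extra samples, slides or reader are needed.

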**5. Variables to collect:**

- Demographic variables
- Conditions that might increase the risk of bleeding like aspirin or renal insufficiency.
- Number of Lymph nodes sampled per patient
- Lymph node size on CT and EBUS.
- Lymph node location.
- ROSE assessment for sample adequacy per each needle pass.
- ROSE assessment for diagnostic yield per each needle pass.
- Final diagnosis
- Physician's satisfaction
- Complications

**6. Data Collection and Monitoring:** Data will be collected prospectively using a data base specially constructed for the purpose.

**6.1.** Study data will be collected and managed using REDCap (Research Electronic Data Capture) electronic data capture tools hosted at MD Anderson. REDCap ([www.project-redcap.org](http://www.project-redcap.org)) is a secure, web-based application with controlled access designed to support data capture for research studies, providing: 1) an intuitive interface for validated data entry; 2) audit trails for tracking data manipulation and export procedures; 3) automated export procedures for seamless downloads to common statistical packages; and 4) procedures for importing data from external sources. In the case of multi-center studies REDCap uses Data Access Groups (DAGs) to ensure that personnel at each institution are blinded to the data from other institutions. REDCap (<https://redcap.mdanderson.org>) is hosted on a secure server by MD Anderson Cancer Center's Department of Research Information Systems & Technology Services. REDCap has undergone a Governance Risk & Compliance Assessment (May 2014) by MD Anderson's Information Security Office and found to be compliant with HIPAA, Texas Administrative Codes 202-203, University of Texas Policy 165, federal regulations outlined in 21CFR Part 11, and UTMDACC Institutional Policy #ADM0335.

Those having access to the data include the study PI and research team personnel. Users are authenticated against MDACC's Active Directory system. External collaborators are given access to the database once approved by the PI, with their access expiring in 6 months but renewable in 6 months increments at the request of the PI. The application is accessed through Secure Socket Layer (SSL). All protected health information (PHI) will be removed from the data when it is exported from REDCap for analysis. All dates for a given patient will be shifted by a randomly generated number between 0 and 364, thus preserving the distance between dates. Dates for each patient will be shifted by a different randomly generated number.

Following publication study data will be archived in REDCap. Since study data may be useful for future research studies performed under separate IRB approved protocols, study data will be archived indefinitely in REDCap. Since REDCap is a secure electronic database with controlled access, and because patient identifiers may be needed to link study data to data from other sources under future IRB approved protocols, patient identifying information will be retained in the archived database.

7. **Sample size:** A sample size of 200 lymph nodes is planned to provide a precise estimate of concordance between 22-G needle and 25-G needle in terms of adequacy and diagnosis. We expect the concordance (as indicated in Table 1) to be greater than 90%. Using the following hypothesis test:  $H_0: p \leq 90\%$  versus  $H_a: p > 90\%$  using a one-sample test.

Table 1. Summary of Concordance for 22 and 25-gauged needles

|                 |              | 22 gauge needle |              |
|-----------------|--------------|-----------------|--------------|
|                 |              | Adequate        | Not adequate |
| 25 gauge needle | Adequate     | a               | b            |
|                 | Not adequate | c               | d            |

$$\text{Concordance} = (a + d)/N$$

We plan on assessing 200 lymph nodes with 3 interim looks. After the observance of every 50 lymph nodes sequentially, the final analysis plans to use all 200 lymph nodes. Using a one sample binomial test (East v5) to guide the trial, the test parameters considered were as follows: i) 2-Sided, 0.05 Significance Level, and Power of 88%. Assessments will be considered for both futility and superiority. The Lan and DeMets with O'Brien-Flemming type stopping boundaries were used to generate the p-values required to pause the trial for additional patient entry under the circumstances that a futility or superiority boundary is crossed. Note that the stopping boundaries are estimates to guide the trial because the sample size is relative to the number of lymph nodes (not patients), and it is highly expected that one patient will contribute multiple lymph nodes for analysis.

Table 2.

|   | Plan characteristics |
|---|----------------------|
| Assumed Difference                        | 96% versus 90%       |
| 2-sided Test                              |                      |
| Nominal Significance Level                | 0.05                 |
| Power                                     | 88%                  |
| 1 st Interim Analysis (N = 50) |                      |
| P-value to stop for superiority           | < 0.001              |

|  |       |
|--|-------|
| P-value to stop for futility                 | 0.998 |
|  |       |
|  |       |
| 2 nd Interim Analysis (N = 100)   |       |
| P-value to stop for superiority              | 0.003 |
| P-value to stop for futility                 | 0.558 |
|  |       |
|  |       |
| 3 rd Interim Analysis (N = 150)   |       |
| P-value to stop for superiority              | 0.018 |
| P-value to stop for futility                 | 0.159 |
|  |       |
|  |       |
| Final Analysis (N =200) lymph nodes acquired |       |
| P-value to reject H 0             | 0.044 |
|  |       |
|  |       |

We estimate an a priori concordance between the two techniques of 96% (or 192/200), which would yield a 95% CI with 2.25 percentage points as the distance from the observed proportion to the upper limit of the 95% CI, and 3.73 percentage points as the distance from the observed proportion to the lower limit of the 95% CI (noting that the Clopper-Pearson exact 95% CI is not symmetric).

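### Section 7 tests for concordance above 90%, but Table 2 is a symmetric two-sided design: as printed, 45/50 stops for futility, 44/50 does not, and low concordance meets the superiority p-values

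*Combined protocol and SAP*

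**What the plan says.** Section 7 sets a one-sample test of H0: p ≤ 90% against Ha: p > 90%, and introduces it with "We expect the concordance (as indicated in Table 1) to be greater than 90" per cent. The design parameters that follow are "i) 2-Sided, 0.05 Significance Level, and Power of 88" per cent. Table 2 repeats that the test is two-sided, and section 8 again uses a two-sided 0.05 level.

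Three interim looks are planned, at 50, 100 and 150 nodes, with the final analysis at 200. "Assessments will be considered for both futility and superiority". Lan-DeMets boundaries of O'Brien-Fleming type "generate the p-values required to pause the trial for additional patient entry under the circumstances that a futility or superiority boundary is crossed". Table 2 gives these only as p-values, with no sign, count or direction:

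- Rows labelled "P-value to stop for superiority": <0.001, 0.003 and 0.018. The final p-value to reject H0 is 0.044.
- Rows labelled "P-value to stop for futility": 0.998, 0.558 and 0.159.

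Because one patient may contribute several nodes, section 7 adds that "the stopping boundaries are estimates to guide the trial".

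**The concern.** A two-sided p-value measures distance from 90% in either direction. A futility rule that stops when this p-value is large therefore stops only near 90% and lets worse results continue. A superiority rule that stops when it is small is met by very low concordance as well as by very high. Neither fits Ha: p > 90%.

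These p-values decide whether patient entry is paused. Poor agreement between the needles is the case a futility rule exists for, and there the printed rule either fails to stop the study or stops it under the wrong label.

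**Working it through.** **Inputs (section 7, Table 2).** p0 = 0.90, p1 = 0.96; looks at 50, 100, 150 and 200 nodes; two-sided 0.05; power 88%; the printed p-values. Nodes are taken as independent unless stated.

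**1. Reproducing the superiority p-values.** Cumulative spending per tail at information fraction t is 2[1 − Φ(z₀.₀₁₂₅/√t)]. At t = 0.25 this is 2[1 − Φ(2.241/0.5)] = 0.0000074, so the two-sided p is 0.000015. The four looks give z = 4.334, 2.964, 2.360 and 2.015, that is two-sided p = 0.000015, 0.0030, 0.0183 and 0.0439. Table 2 prints <0.001, 0.003, 0.018 and 0.044. The match is on the two-sided scale.

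**2. Reproducing the futility p-values.** Take a symmetric inner wedge |z| ≤ c on the null-variance z, with variance 0.96 × 0.04 under the alternative and type II spending 4[1 − Φ(z_{β/4}/√t)]. The value β = 0.119 was fitted; the plan states 88% power.

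- At t = 0.25 the spend is 4[1 − Φ(1.885/0.5)] ≈ 0.0003.
- At 50 nodes and p = 0.96, z has mean 0.06√50/0.3 = 1.414 and SD √0.0384/0.3 = 0.653. Its density at zero is φ(2.165)/0.653 ≈ 0.0586, so 2c × 0.0586 = 0.00033 and c = 0.0028. The two-sided p is 0.998.
- The later looks give c = 0.585 and 1.407 (p = 0.559 and 0.159), closing at 0.044, with normal-approximation power 88.1%.

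Table 2 prints 0.998, 0.558, 0.159 and 88%. The table is a coherent symmetric design.

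**3. What the printed p-values mean as counts.** Score test: z = (x − 0.9N)/√(0.09N), p = 2[1 − Φ(|z|)]. At N = 50, √4.5 = 2.121:

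- 45/50: z = 0, p = 1.000, stops for futility.
- 44/50: z = −1/2.121 = −0.471, p = 0.637, does not.
- 50/50: z = 5/2.121 = 2.357, p = 0.018, misses <0.001.
- 38/50: z = −7/2.121 = −3.300, p = 0.00097, meets <0.001.

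| Nodes | Futility met at | Superiority / reject H0, above 90% | Same p-value, below 90% |
|---|---|---|---|
| 50 | 45 only | none attainable | ≤38 |
| 100 | 89–91 | ≥99 | ≤81 |
| 150 | 130–140 | ≥144 | ≤126 |
| 200 | – | ≥189 | ≤171 |

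With a doubled exact p the futility window at 100 becomes 88–92 and the low-side limits become 36, 79, 125 and 170. On either method 44/50, 87/100 and 129/150 do not stop for futility although they are worse than counts that do.

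**4. Behaviour when concordance is poor (exact binomial over the four looks).** The one-directional rule shown is futility at ≤43/50, ≤91/100 and ≤140/150.

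| True concordance | Printed rule: futility stop | Printed rule: success p-value met from below | One-directional rule: futility stop, mean nodes |
|---|---|---|---|
| 85% | 39% (doubled exact 42%) | 53% (doubled exact 46%) | >99.9%, 69 |
| 80% | 5% | 94% | >99.9%, 55 |

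At 85% the printed rule has a mean of 164.5 nodes if low-side crossings are ignored, and 133–137 if they also stop the study.

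**5. Error and power (superiority none/99/144/189).**

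| Futility rule | Upper error at 90% | Power at 96% |
|---|---|---|
| Printed, score p | 0.016 | 85.8% |
| Printed, doubled exact p | 0.016 | 85.1% |
| ≤45, ≤91, ≤140 | 0.016 | 85.4% |
| ≤43, ≤91, ≤140 | 0.017 | 87.5% |
| none at 50, then ≤91, ≤140 | 0.017 | 87.6% |
| no futility | 0.019 | 89.6% |

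The shortfall comes mainly from discreteness at 50 nodes: the wedge was meant to spend about 0.0003 of type II error, but P(X = 45 | 50, 0.96) = 3.5%.

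**6. Clustering check.** Assuming pairs of nodes per patient and an intraclass correlation of 0 to 0.3, the printed rule still stops only 39–42% for futility at true 85%.

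**The case against.** **The direction is implied.** Ha, the superiority label and the 96% versus 90% assumption all point upwards, and a two-sided p-value is often reported for a directional claim. Nobody applying Ha would call 38/50 a success. That stands, and it limits the low-side problem to wording.

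**The two harms belong to different readings.** If low-side crossings do pause entry, then at true 85% about 39% stop for futility and another 39% stop at an interim from below, about 78% in all; the harm is then a wrong label. The 164.5-node mean belongs to the other reading. The two should not be added.

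**The failure to stop is not uniform below 90%.** Ignoring low-side crossings, the printed futility windows stop 76% of trials at true 88% and 88% at true 90%. The rule fails at about 85% and below.

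**Reading the futility values as upper-tail p-values** gives workable limits of ≤38/50, ≤89/100 and ≤138/150, with exact power 89.6% and 99.7% stopping early at true 85%. But Table 2 says two-sided, the two-sided wedge reproduces its values at the stated power, and the one-sided scale comes near them only at about 99% power. The plan does not state this reading.

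**The boundaries are only a guide.** The reason given is clustering of nodes; it supplies no direction.

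**No single futility set follows from the plan.** This also stands. Other spending choices give ≤43/≤92/≤140 (power 86.7%) or about ≤44/≤92/≤140 (86.4%).

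**Conclusion.** The concern holds, and the rules should be corrected. Table 2 is a coherent two-sided design, but as printed it does not implement a test of p > 90%. Supplying the direction repairs the superiority rule. It does not repair futility at 50 nodes: the value 0.998 either stops 45/50 alone or, carried over as ≤45/50, lowers exact power to 85.4%. Under the printed rule exact power is 85.1–85.8% against the stated 88%, and at true concordance of 85% futility stops 39% of trials where a one-directional rule would stop over 99.9%.

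The planned 200 nodes are not in question. Nor is the final decision: the plan is explicitly two-sided, and 188/200 does not reject (doubled exact p = 0.064; Clopper-Pearson 89.8% to 96.9%), while 189/200 does (p = 0.034; 90.4% to 97.2%).

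The operating figures assume independent nodes and that the stops are followed. The symmetric origin of Table 2 is inferred from reproducing its p-values; the count-level results need only its two-sided label.

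**What to change.** In section 7:

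- State one test: two-sided 0.05 with success only above 90% (one-sided 0.025), using an exact binomial or null-variance score statistic. Say that 188/200 does not reject and 189/200 does.
- Print superiority as counts: none attainable at 50, then ≥99/100, ≥144/150 and ≥189/200.
- Print futility as maximum counts, so that every lower count also stops. The same β spending applied in one direction gives z = −0.81, 0.59 and 1.41, that is ≤43/50, ≤91/100 and ≤140/150. This is one valid derivation; the sponsor may regenerate the limits in its design software. Alternatively drop futility at 50 nodes and keep the other two limits, which raises the mean from 69 to 101 nodes if true concordance is 85%.
- Do not convert 0.998 to ≤45/50.
- State whether futility is binding, and that the figures hold for independent nodes. In the paired-node check, the upper error with 43/91/140 rises from 0.017 to 0.031 and power falls from 87.5% to 84.2% as the intraclass correlation goes from 0 to 0.3.
- State which concordance the boundaries govern. Table 1 and 4.8.6 point to adequacy; 2.1 names adequacy and diagnostic yield, and section 7 opens with a "precise estimate of concordance between 22-G needle and 25-G needle in terms of adequacy and diagnosis".

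The cost is a rewritten Table 2 and a few sentences, with no extra patients, nodes or data. The plan would have to acknowledge that no superiority stop exists at 50 nodes (none was attainable above 90%) and that exact power with futility followed is 87.5%, slightly under 88%.
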